9.6 Protocol Deviations

Deviations from the protocol will be recorded appropriately. Protocol deviations will include the following:

- Subjects who did not give appropriate Informed Consent
- Subjects enrolled who did not meet the inclusion/exclusion criteria
- Subjects who took disallowed or prohibited medications
- Subjects who were not 80% - 105% treatment compliant
- Key endpoint non-compliance: TMC, UHDRS Behavior, HADS, C-SSRS, UPDRS, SDQ, BARS or ESS not performed for 2 or more consecutive expected visits
- Subjects who were administered the wrong study treatment
- Subjects who were administered an incorrect dose or an incorrect starting dose for switch cohort subjects (a dose adjustment would not be considered an incorrect dose)
- Missing safety endpoints at any visit: SDQ, BARS, HADS, or C-SSRS
- Missing lab tests, PK sampling, vital sign and ECG at any visit
- Out of protocol-specified window visits

A listing of protocol deviations will be provided.

9.7 Efficacy Analyses

For TMC and the total motor score of the UHDRS, the Rollover and Switch cohorts will be analyzed separately through Week 8. Descriptive statistics will be presented by visit for the actual data and for the changes from baseline, including 95% confidence intervals for the true mean changes from baseline. For the Switch cohort, the baseline value used for calculating change from baseline for TMC and the total motor score will be the mean of the values from the Screening and Baseline visits. These analyses will be repeated for TMC using data at scheduled visits only and also only using subjects with a TMC score at all scheduled visits up to Week 15.

In addition, for TMC and the total motor score, descriptive statistics will be presented by visit for the actual data and the changes from Week 8, including 95% confidence intervals for the true mean changes from Week 8. Subjects without a Week 8 assessment will be excluded from the analysis. This analysis will be done for the prior SD-809 subjects in the rollover cohort, prior placebo subjects in the rollover cohort, the switch cohort, and the two cohorts combined.

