Subjects Enrolled from the SD-809-C-15 Study (Rollover): Subjects who have successfully completed Study SD-809-C-15 may be eligible to rollover directly into this study after they complete a 1-week washout period and the Week 13 evaluation of Study SD-809-C-15. To reduce subject burden, the Week 13 evaluation will provide some Baseline data for the present study. Additional evaluations required as part of the SD-809-C-16 study may be completed on the same day as the Week 13 visit of the SD-809-C-15 study after SD-809-C-16 informed consent/assent is obtained. If subjects are unable to enroll at the Week 13 visit they will have up to 3 weeks to complete the additional evaluations for Baseline or the subject will not be eligible to enroll in this study. In addition, following informed consent/assent, prior data from Study SD-809-C-15 can be used in this study as part of the subject’s medical history information.

As Rollover subjects will have discontinued study drug (SD-809 or placebo) for at least 1 week at completion of the SD-809-C-15 study, they will undergo titration on SD-809. During titration, the Investigator, in consultation with the subject and caregiver, will determine when an adequate level of chorea control has been achieved. The dose of SD-809 may be adjusted (upward or downward), in increments of 6 mg per day (each week) (6 mg/day or up to 12 mg/day after a total daily dose of 48 mg is reached), until there is adequate control of chorea, the subject experiences a protocol defined “clinically significant” adverse event, as outlined above, or the maximal allowable dose is reached. If a subject experiences a “clinically significant” AE attributable to SD-809, the Investigator will determine if a dose reduction or suspension is necessary. Although subjects will enter the long-term treatment period after Week 2, titration may occur through Week 8 to optimize dose level. Additional dose adjustments may be made after Week 8 if clinically indicated.

Long-Term Treatment Period: During long-term treatment, further dose adjustments of SD-809 may be made, if necessary, but not more often than weekly. Dose adjustments should be based on all available information including the subject's and caregiver's reports of adverse events and chorea control, information from rating scales, and all safety evaluations. The Long-Term Treatment Period will continue until SD-809 becomes commercially available in the U.S.

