8.5 Handling of Missing Data

8.5.1 Missing Data for Individual Items of an Instrument

For the Total Motor Score and the TMC Score of the UHDRS, missing data items will be imputed, provided that at least 80% of the items for the corresponding score are nonmissing. In such cases, the value(s) of the missing item(s) will be imputed by carrying forward the most recent nonmissing value of the corresponding item. However, if more than 20% of the items for the score are missing, the score will be treated as missing.

For all other missing data items, the missing data items will remain missing and will not be imputed, and only observed data will be summarized.

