8.5.2 Missing Endpoint Data

Missing endpoint data will not be imputed, and only observed data will be summarized.

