8.9 Analysis Visit Windows

For efficacy and safety by-visit analyses, data collected at post baseline scheduled visits will be included using their nominal visit. Data collected at early termination, end of treatment, and unscheduled visits will be assigned to a visit window as described below. All scheduled visits will be assigned a target study day; for the determination of target days, weeks will be assumed to have 7 days. Thus, Week 4 would have a target day of $4 \times 7 = 28$ days. For each visit, a visit window will be assigned so that anything from the midpoint to the prior target day to the midpoint to the following target day will be assigned to that visit window as shown in Table 3 below. The following rules concerning visit windows and selecting records for analysis will be used:

1. Scheduled visit has precedence.

2. If there are multiple records of the same scheduled visit, the record closest to the target day will be used for analysis. If two records are equidistant, then the earlier one will be used.
3. For a given visit, if there is no data from a scheduled visit, data from an unscheduled visit that occurs in the visit window will be used for analysis.

Table 3: Analysis Visit Window

| Visit | Target Day | Visit Window |
|-----------------------------|------------|--------------|
| Screening | -5 | (--, -5) |
| Screening Telephone Contact | -2 | (-4, -2) |
| Baseline | -1 | (-1, -1) |
| Week 1 | 7 | (1,10) |
| Week 2 | 14 | (11-17) |
| Week 3 | 21 | (18, 24) |
| Week 4 | 28 | (25, 31) |
| Week 5 | 35 | (32, 38) |
| Week 7 | 49 | (39, 52) |
| Week 8 | 56 | (53, 80) |
| Week 15 | 105 | (81, 150) |
| Week 28 | 196 | (151, 241) |
| Week 41 | 287 | (242, 332) |
| Week 54 | 378 | (333, 423) |
| Week 67 | 469 | (424, 514) |
| Week 80 | 560 | (515, 605) |
| Week 93 | 651 | (606, 697) |
| Week 106 | 742 | (698, 787) |
| Week 119 | 833 | (788, 879) |
| Week 132 | 924 | (880, 970) |
| Week 145 | 1015 | (971, 1060) |
| Week 158 | 1106 | (1061, 1152) |
| Week 171 | 1197 | (1153, --) |

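### The long-term change-from-Week-8 means and CIs for TMC and total motor score use observed cases only, with no attrition check after Week 15, and may understate worsening if worsening subjects leave

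*SAP*

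**What the plan says.** SAP 7.1 names change from Week 8 in TMC and total motor score as an efficacy endpoint alongside change from baseline. SAP 8.10 records that both scores were moved from safety to efficacy.

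The second paragraph of SAP 9.7 plans by-visit descriptive statistics for the observed values and "the changes from Week 8, including 95% confidence intervals for the true mean changes from Week 8". Entry is conditional: "Subjects without a Week 8 assessment will be excluded from the analysis". Rows are planned for prior SD-809, prior placebo and Switch subjects, and for the two cohorts combined.

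On missing data, SAP 8.5.2 states: "Missing endpoint data will not be imputed, and only observed data will be summarized". SAP 8.5.1 provides for TMC and total motor score that "the value(s) of the missing item(s) will be imputed by carrying forward the most recent nonmissing value of the corresponding item" when at least 80% of items are present. That repairs incomplete assessments, not missed visits or visits after withdrawal.

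The one fixed-cohort repeat is in the first paragraph of SAP 9.7, on change from baseline. It is for TMC and is made "also only using subjects with a TMC score at all scheduled visits up to Week 15".

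Follow-up is open-ended. SAP Section 4 says: "The Long-Term Treatment Period will continue until SD-809 becomes commercially available in the U.S". The visit-window table in SAP 8.9 runs to Week 171.

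**The concern.** Each long-term mean is taken over a different and generally shrinking set of subjects. The interval is described as one for the true mean change, but it estimates the mean only among those with data at that visit. The two coincide only if having data is unrelated to change.

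Some link between change and leaving is plausible. Protocol 1.1 describes HD as progressive. Protocol 6.13 lists intolerable adverse events, need for interfering medication and inability to comply among the withdrawal reasons. Protocol 6.9.1 bars antipsychotics and amantadine throughout.

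At stake is how a flat curve after Week 8 is read. It could reflect stable chorea, or the departure of subjects who were worsening, and the planned table cannot separate the two. SAP Section 2 envisages these results in regulatory submissions or manuscripts.

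**Working it through.** **Document arithmetic.** Planned N is 36 + 80 = 116 (Protocol Synopsis). Week 158 is day 158 × 7 = 1106, as in the SAP 8.9 table. Time from Week 8 to Week 158 is (158 − 8)/52 = 2.88 years. Neither document gives a dropout rate, a TMC drift, an SD, or a link between change and withdrawal, so there is no planned figure to reproduce. Everything below rests on assumptions and compares the observed-case mean at Week 158 with the mean of everyone who had a Week 8 value.

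**Check 1: large simulated cohort (400,000 per scenario).** Assumed: drift 1.0 point/year, slope SD 1.0, visit error SD 2.0, Week 8 value taken as error-free, baseline dropout 4% per 13-week interval, odds of leaving multiplied by a fixed factor per point of worsening at the last visit. True mean: 1.0 × 2.88 ≈ 2.9.

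- Factor 1.35: 44% remain; observed mean 1.9.
- Factor 1.16: observed mean 2.5.
- Factor 1.35 with slope SD 1.5: observed mean 0.9.
- No link: observed mean 2.9. Baseline dropout alone over 11 intervals would leave 0.96^11 = 64%; the fall to 44% is the extra loss among worsening subjects.

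**Check 2: trial-sized (N = 116, 300 runs per scenario).** Assumed: all 116 have a Week 8 value, slope SD 1.5, visit error SD 2.0 including at Week 8, dropout hazard ratio (HR) per point of last observed change relative to the cohort mean. Values from the visit at which a subject leaves are counted, to mimic SAP 8.9.

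| Dropout/year | HR per point | Left at Week 158 | Observed vs true 2.88 (CI coverage) | Observed vs true 1.44 (CI coverage) |
|---|---|---|---|---|
| 10% | 1.1 | 87 | 2.55 (93%) | 1.10 (92%) |
| 10% | 1.2 | 84 | 2.27 (82%) | 0.79 (76%) |
| 20% | 1.0 | 65 | 2.89 (94%) | 1.40 (96%) |
| 20% | 1.1 | 63 | 2.16 (82%) | 0.75 (84%) |
| 20% | 1.2 | 60 | 1.61 (51%) | 0.13 (46%) |
| 30% | 1.2 | 42–43 | 1.00 (30%) | −0.40 (31%) |

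True values of 2.88 and 1.44 correspond to drifts of 1.0 and 0.5 points/year.

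- With no link, coverage was 93–96% at every dropout rate.
- With reverse selection (HR 1/1.1, 20%/year), the observed mean was 3.47 against 2.88, so worsening was overstated.
- With a random administrative cut-off plus unrelated dropout, the mean was 2.77 against 2.88 with 96% coverage. About 12 subjects remained: precision is lost, but there is no material bias.

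**Does a likelihood-based estimate help?** In Check 2, generalised least squares on all observed visits gave 2.87 to 2.94 against 2.88, and 1.39 to 1.49 against 1.44, wherever worsening or nothing drove dropout. It was given the true covariance and a linear trend, which flatters it. Under Check 1 assumptions with n = 116 (40 replicates), a random-slope mixed model with categorical visit gave 2.84 against 2.88, with an observed-case mean of 1.88. That model also matches how the data were generated. Both results hold because dropout depended only on observed values.

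**The case against.** A reader might infer that these intervals do hide worsening and do not cover the cohort mean. The documents do not support that. They give no dropout rate and no link between TMC change and withdrawal; bias can be nil or reversed. Loss of chorea control is not a listed withdrawal reason in Protocol 6.13. Protocol 6.3 lets subjects who become non-ambulatory stay, and Protocol 5.2.4 allows dose adjustment during long-term treatment. These features temper the assumed mechanism, and the simulations include neither.

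It would also be too strong to say that only subjects still attending are counted. SAP 8.9 states: "Data collected at early termination, end of treatment, and unscheduled visits will be assigned to a visit window as described below". This stands as description, although it removed little bias in Check 2 (2.16 with those values, 2.14 without, at HR 1.1 and 20%/year).

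Other parts of the defence stand. Numbers of observations are in every continuous summary (SAP 8.7), withdrawal reasons are tabulated (SAP 9.1), and dose is summarised for subjects with a TMC score at the visit (SAP 9.8). A shift in cohort mix would show in the separate rows. Loss from the calendar-driven end may be purely administrative. SAP 8.1 plans no formal analyses, and without a control arm a flat curve cannot establish maintained benefit under any model. Nor does SAP 9.7 say why it repeats the TMC analysis to Week 15, so that repeat does not show that its authors saw an attrition problem.

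What survives is narrower. The interval's stated target is wider than what it estimates, and nothing planned shows how far the two may differ after Week 15.

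**Conclusion.** The point holds as a conditional one and is worth acting on. If worsening raises dropout, the Week 158 mean could be about 1.9 to 2.5 where the cohort truth is 2.9, an understatement of 0.4 to 1.0 point at a drift of 1 point per year. Steeper slope variation or a stronger link makes it larger; weaker dependence makes it smaller; no dependence removes it. Only the direction under each assumption, and the rough size, should be cited. The claim that worsening is in fact hidden is not established.

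**What to change.** In SAP 9.7:

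1. Keep the observed-case table, and label its intervals as the mean change among subjects observed at that visit.
2. Add, as a supportive analysis for both scores, a repeated-measures mixed model on all post-Week-8 data with visit, cohort, visit-by-cohort and the Week 8 value. Pre-specify a parsimonious covariance, such as random intercept and slope, or a stated fallback order. The SAP 8.9 table has 13 visits after Week 8 (15 to 171), so an unstructured matrix would need 13 × 14/2 = 91 parameters from about 116 subjects. Limit the model to visits with adequate n, by a stated rule.
3. Summarise last on-treatment change from Week 8 by completion status, separating administrative study end from other withdrawal.
4. Add a simple delta-adjusted sensitivity analysis.

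The cost is SAP text and a few tables. The model assumes data are missing at random given observed values. That is weaker than what is needed to read observed-case means as cohort means, and the delta adjustment probes it. The model does not restore subjects lost before Week 8. A fixed-cohort table to Week 54 could serve as a diagnostic, but that cohort is itself selected, so it corrects nothing.

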9.8 Analysis of Dose Level

Total daily dose level (mg) at Week 1 (Switch cohort)/Week 2 (Rollover cohort), and each scheduled visit will be summarized for each cohort using descriptive statistics. The baseline tetrabenazine dose level will be summarized for the Switch cohort. In addition, the number and percentage of subjects at each dose level will be summarized for each visit.

The total daily dose level will also be summarized by visit using descriptive statistics for the subjects with a corresponding TMC score at the given visit.

9.9 Safety Analyses

Safety will be assessed using the Safety Population.

9.9.1 Adverse Events

Adverse events will be coded using version 16.1 of the Medical Dictionary for Regulatory Activities (MedDRA); the MedDRA version will be noted in the CSR. Treatment-emergent AEs (TEAEs) are events that 1) begin after treatment with study drug in the current study and that are not present at baseline or 2) if present at baseline, have worsened in severity. For AEs with missing start dates, the AE will be considered treatment-emergent unless there is additional information indicating that the AE started prior to the first treatment. All analyses of TEAEs will be performed separately for TEAEs that occurred during the titration period (for Rollover subjects only), during the dose-adjustment period (for Switch subjects only), during the extended dose-adjustment period (for Switch subjects only), during the stable dose period, and during the entire treatment period. To be conservative, all adverse events that occurred during the follow-up period will be counted as events that occurred during the last available treatment period. In order to be included in the analysis for a given time period, a subjects must have at least one visit during the time period.

For the Switch cohort, an overview of AEs occurring during the Screening period will present the number and percentage of subjects in the following categories:

- Any AEs
- Any serious AEs (SAEs)
- Any severe AEs
- Any AE(s) leading to death

An overview of TEAEs will present the number and percentage of subjects in the following categories:

- Any TEAEs
- Any serious TEAEs

-
- Any severe TEAEs
 - Any treatment-related TEAEs
 - Any TEAEs resulting in dose reduction
 - Any TEAEs resulting in dose suspension
 - Any TEAEs resulting in withdrawal from the study
 - Any treatment-related TEAEs resulting in withdrawal from the study
 - Any TEAEs resulting in dose reduction, dose suspension, or withdrawal from the study
 - Any TEAE(s) leading to death

TEAEs, serious TEAEs, TEAEs that led to dose reduction, TEAEs that led to dose suspension, TEAEs that led to withdrawal from the study, TEAEs that occurred in at least 4% of Rollover or Switch cohort subjects in the Safety Population across all time periods, will be summarized at the subject level by MedDRA system organ class (SOC) and preferred term using frequencies and percentages.

Exposure adjusted incidence rates (number of patients with an event per person-year) will also be presented for the above TEAE overview categories, all preferred terms, and selected AEs of interest by patient cohort and study (First Active in C15, First Placebo in C15, Rollover in C16, and Switch in C16). AEs of agitation, somnolence, insomnia, anxiety and fall will be defined as events with matched preferred terms. In addition, AEs with selected preferred terms will be combined into the AEs of interest as follows:

- Akathisia and Restlessness: Akathisia, Hyperkinesia, Psychomotor hyperactivity, Restlessness, Agitation
- Dysphagia: Aphagia, Dysphagia
- Parkinsonism: Akinesia, Bradykinesia, Cogwheel rigidity, Freezing phenomenon, Hypertonia, Masked facies, Muscle rigidity, On and off phenomenon', Parkinsonian crisis, Parkinsonian gait, Parkinsonian rest tremor, Parkinsonism, Parkinson's disease, Resting tremor
- Suicidality: Completed suicide, Depression suicidal, Intentional overdose, Intentional self-injury, Poisoning deliberate, Self-injurious ideation, Suicidal behavior, Suicidal ideation, Suicide attempt.
- Depression: all preferred terms containing “depression”

Incidence rate will be calculated as:

Number of patients with given event/ Person-years for the event

Person-years for a selected event are defined as the sum of exposure days across all subjects divided by 365.25. Subjects with an event of the given type contribute days from the date of their first treatment dose until the date of the first event of the given type. Subjects without an event of the given type contribute days from date of their first treatment dose until their treatment end date. Events that occurred after the last dose date of each study period were not included.

TEAEs and treatment-related TEAEs, categorized by system organ class, preferred term, and maximum severity (mild, moderate, or severe), will be summarized by study period using counts and percentages. In addition, TEAEs, categorized by system organ class, preferred term, and relationship to study drug (unrelated, related), will be summarized by study period using counts and percentages. TEAEs that are classified as possibly, probably, or definitely related to study drug on the AE eCRF, or for which the relationship to study drug is missing, will be considered treatment related. Unrelated AEs include those classified as unrelated or unlikely related on the AE eCRF.

Subjects receiving a strong CYP2D6 inhibitor or who are poor CYP2D6 metabolizers are considered to have impaired CYP2D6 function. The following AE analyses will be repeated by impaired CYP2D6 function category at baseline (subjects receiving a strong CYP2D6 inhibitor at Baseline, subjects not receiving a strong CYP2D6 inhibitor at Baseline, CYP2D6 poor metabolizers, non-CYP2D6 poor metabolizers, subjects with impaired CYP2D6 function, and subjects without impaired CYP2D6 function):

- Overview of TEAEs
- TEAEs by SOC and preferred term

For TEAE summaries, if a subject has more than one TEAE within a preferred term, the subject is counted once in that preferred term at the maximum severity and at the closest relationship to study drug. If a subject has more than one TEAE within a system organ class, the subject is similarly counted once in that system organ class.

Complete listings of all AEs will be provided. In addition, data listings of all SAEs, AEs leading to withdrawal from the study, and AEs leading to death will also be provided.

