8.1 Analysis Populations

Safety Population: The safety population will include all subjects who were administered any study drug. Subjects who are assigned a subject number but withdrew prior to dosing will not be included in the safety population. If relevant, details of their participation and reason for withdrawal will be listed separately in the study report.

All summaries of safety endpoints will be summarized descriptively in the Safety Population.

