- ** Data (Week 13) from Study SD-809-C-15 will be utilized as part of Baseline assessment. Additional specific activities required at this visit are denoted by an “X”
- 1 Assessment transferred from Screening or Baseline evaluation in Study SD-809-C-15
 - 2 Perform orthostatic blood pressure and pulse after subject is in standing position for at least 3 minutes.
 - 3 Assessments to be completed at Investigator’s discretion
 - 4 Brief physical examination, which includes evaluation of the cardiovascular, respiratory, and abdominal systems.
 - 5 The C-SSRS Since Last Visit version is administered at all visits for Rollover subjects
 - 6 Study medication supply will be ordered (See Operations Manual for further details).
 - 7 Subjects who withdraw early from the study should have a single blood sample collected for PK at the Early Termination Visit if the last dose was within the prior 48 hours, if possible. Subjects who experience an SAE should have a single blood sample collected for metabolites of SD-809 within 48 hours of SAE, if possible.
 - 8 For subjects on allowed doses of citalopram or escitalopram:
 - Week 2: A 12-lead ECG is required at this visit.
 - Week 4: If the dose of study drug has been increased since the last ECG, a 12-lead ECG is required at this visit.
 - 9 After Week 28, perform clinic visits every 13 weeks until the End of Treatment Visit. Obtain safety labs and urine pregnancy test every 26 weeks after Week 28, and perform UHDRS-TFC every 52 weeks after Week 28.
 - 10 For subjects requiring an Unscheduled Clinic Visit for any reason, assessments denoted with X should be performed; all other assessments are as indicated at Investigator’s discretion (see Section 6.5 of the protocol).

5 Data Management

Complete details of data management will be described in a separate Data Management Plan.

6 Definition of Population

Safety Population: The Safety Population will include all subjects who were administered any study drug. Subjects who are assigned a subject number but withdrew prior to dosing will not be included in the Safety Population. If relevant, details of their participation and reason for withdrawal will be listed separately in the CSR.

Unless specified otherwise, all data will be summarized for the Safety Population. In addition, two subsets of the Safety Population are defined:

- Rollover Cohort: Successfully completed SD-809-C-15 (First-HD) prior to enrollment into SD-809-C-16 (ARC-HD)

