7.2 Safety Endpoints

Safety and tolerability will be assessed throughout the study by monitoring the following:

- Incidence of adverse events (AEs), serious AEs (SAEs), severe AEs, drug-related AEs, and AEs leading to withdrawal during the following periods:
 - The entire post-baseline period
 - During the Titration Period (from Day 1 to the end of Week 8) in Rollover subjects
 - During the Dose-Adjustment Period (from Day 1 to the end of Week 4) in Switch subjects
 - During the Extended Dose-Adjustment Period (from Day 1 to the end of Week 8) in Switch subjects who undergo dose adjustment between Weeks 4 and 8 (if at least 10% of Switch subjects have had a dose adjustment between Week 4 and Week 8)
 - During the Stable-Dose Period (Week 8 to end of study)
- Observed values and changes from baseline in clinical laboratory parameters (hematology, chemistry, and urinalysis)
- Observed values and changes from baseline in vital signs
- Observed values in ECG parameters and abnormal findings

- Numbers of subjects with QTcF values > 450 msec, > 480 msec, > 500 msec
- Counts and percentages for Columbia Suicide Severity Rating Scale (C-SSRS)
- Observed values and changes from baseline in the following:
 - Unified Huntington Disease Rating Scale (UHDRS)
 - Unified Parkinson's Disease Rating Scale (UPDRS) (dysarthria)
 - Barnes Akathisia Rating Scale (BARS)
 - Hospital Anxiety and Depression Scale (HADS)
 - Epworth Sleepiness Scale (ESS)
 - Montreal Cognitive Assessment (MoCA[®])
 - Swallowing Disturbance Questionnaire (SDQ)
- Duration of time to achieve a stable dose of SD-809, defined as the number of days from Day 1 until the first day at which the subject was taking the dose level they were receiving at Week 8.

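### SAP 9.9.1 admits a subject to a TEAE period by attendance, not dosing, so a few dosed subjects with recorded events could drop out of the incidence tables

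*SAP*

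**What the plan says.** Protocol 8.1 and SAP section 6 define the same population. In the SAP's words, "The Safety Population will include all subjects who were administered any study drug". Protocol 8.1 adds that "All summaries of safety endpoints will be summarized descriptively in the Safety Population", and SAP 9.9 opens with "Safety will be assessed using the Safety Population". Neither of those two sentences carries an exception. SAP section 6 does allow one: "Unless specified otherwise, all data will be summarized for the Safety Population".

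SAP 9.9.1 then makes entry to each period's analysis conditional: "a subjects must have at least one visit during the time period". The TEAE analyses it governs are those for titration, dose adjustment and extended dose adjustment, and also those "during the stable dose period, and during the entire treatment period". No exception is made for death, loss to follow-up, or an event reported without a visit. SAP 8.10, which lists changes from the protocol's analyses, does not mention the rule.

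The periods are defined twice. SAP 7.2 starts the early ones on Day 1: "During the Titration Period (from Day 1 to the end of Week 8) in Rollover subjects" and "During the Dose-Adjustment Period (from Day 1 to the end of Week 4) in Switch subjects". Its overall period is everything after baseline. SAP 8.8 starts the early periods and the entire treatment period at Baseline, and ends the entire treatment period at the last dose. Both sections start the Stable-Dose Period at Week 8, but 7.2 runs it to the end of the study and 8.8 to the last dose.

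**The concern.** Adverse event data do not depend on a visit. Sites report SAEs within 24 hours of awareness (Protocol 7.4.1) and record adverse events from consent onward (Protocol 7.2.1 and 7.2.2). An early fatal or serious event can therefore be in the database although the subject never had a contact in the period. Under the visit rule, such a subject would be removed only at tabulation, from numerator and denominator together.

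That exclusion can be informative, because an event may be the reason there was no visit. In a study whose first two objectives are safety and tolerability, and whose planned cohorts are about 36 and 80, one removed event can empty a row of the table. The rule also sits oddly beside the sentence before it, which assigns follow-up events to the last treatment period in order to be conservative.

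**Working it through.** The plan states no figure to reproduce, so the check sets the texts side by side and then illustrates the size.

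**Step 1: who can lack an in-period visit?**

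Inputs:
- Switch subjects have their Baseline visit on Day 0 and the first dose on Day 1 (Schedule A, note 1).
- The first post-dose contact is a clinic visit at Week 1 for Switch subjects and a telephone contact at Week 1 for Rollover subjects. Both have target Day 7 (SAP Table 3).
- Table 3 lists telephone-only weeks in its visit column, which suggests that calls count as visits.
- After Week 8 (Day 56) the next scheduled contact is Week 15 (Day 105): 105 − 56 = 49 days.

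| Period | SAP 7.2 definition | SAP 8.8 definition |
|---|---|---|
| Titration, dose adjustment, extended dose adjustment | Starts Day 1. Excludes a subject who dies or is completely lost before the first post-dose contact. | Starts at Baseline. The Baseline visit satisfies the rule; nobody is excluded. |
| Entire period | Post-baseline. Same subject excluded. | Starts at Baseline. Nobody excluded. |
| Stable dose | Starts Week 8. Excludes a subject still on drug who misses the Week 8 visit and dies or is lost before Week 15, with no unscheduled or later contact. | Same subject excluded. |

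**Step 2: size, if it happens.** Assume that k dosed subjects each have a fatal event before any in-period visit, and that no other fatal event occurs. The values k = 1 to 3 are an assumption; the documents give no frequency. Under an any-dose rule the incidence is k/n. Under the visit rule it is 0/(n − k). Exact (Clopper-Pearson) 95% intervals are in brackets.

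| Cohort | k | Any-dose rule | Visit rule |
|---|---|---|---|
| Switch, n = 36 | 1 | 1/36 = 2.8% (0.07 to 14.5) | 0/35 = 0% (0 to 10.0) |
| Switch, n = 36 | 3 | 3/36 = 8.3% (1.8 to 22.5) | 0/33 = 0% (0 to 10.6) |
| Rollover, n = 80 | 1 | 1/80 = 1.25% (0.03 to 6.8) | 0/79 = 0% (0 to 4.6) |
| Rollover, n = 80 | 3 | 3/80 = 3.75% (0.8 to 10.6) | 0/77 = 0% (0 to 4.7) |

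The sample sizes are the protocol's approximate targets (section 3).

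**Step 3: direction.** If the dropped subject had no event and one other subject did, incidence rises slightly: 1/36 = 2.78% becomes 1/35 = 2.86% in Switch, and 1/80 = 1.25% becomes 1/79 = 1.27% in Rollover. The sign of the bias therefore depends on whom the rule removes.

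**The case against.** The strongest reply is that SAP 8.8 is the section that sets period definitions for analyses by period, and it starts the early and entire periods at Baseline. Every dosed subject should have a Baseline visit, so the rule would exclude nobody there. This stands as one of two readings. It does not settle the matter, because 7.2 defines the endpoint periods differently and the SAP does not say which section governs or whether a pre-dose visit satisfies the rule.

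It can also be said that the exception clause in SAP section 6 permits the rule, and that a restricted denominator is proper for later periods, since SAP 8.8 gives early withdrawals no Stable-Dose Period. Both points have force, so a flat contradiction is more than the text supports. What remains is that SAP 9.9 and Protocol 8.1 carry no such exception.

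A reader might infer several stronger things that the documents do not support:
- *That missing the first post-dose visit, or being in hospital for it, excludes a subject.* The test is having no visit at all in the period. Anyone who returns within it qualifies.
- *That an early stopper seen only at an early termination visit drops out of the overall period.* This needs 7.2's start combined with 8.8's end. Under 7.2 that visit counts; under 8.8 Baseline does.
- *That the 7- and 13-week gaps after Week 8 exclude subjects in general.* Both definitions start at Week 8, so on their wording the Week 8 visit can count and its attendees qualify.
- *That Rollover subjects are exposed until the Week 2 clinic visit.* Table 3 points to telephone contacts counting.
- *That the rule can only lower incidence.* Step 3 shows otherwise.
- *That the events disappear from the report.* SAP 9.9.1 lists all adverse events, SAEs and deaths. Its exposure-adjusted rates are taken over all subjects with no visit condition restated, although they omit events after the last dose date and so are not a complete substitute.

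**Conclusion.** The point holds in a limited form. The incidence tables depend on attendance, whereas the stated basis for safety is dosing. For the early and overall periods, exclusion arises only if they start after Baseline, as in SAP 7.2, and then only for death or complete loss within about the first week. For the Stable-Dose Period it arises under either definition, but needs a missed Week 8 visit, continued dosing, and death or loss before Week 15 with no other contact.

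Few subjects are likely to be affected, possibly none. The shift from 1/36 to 0/35, or from 1/80 to 0/79, is an illustration that assumes one such event and no other in the cohort. The problem is possible informative exclusion of subjects with recorded events, not a demonstrated downward bias. It is still worth correcting, because the denominator of the main safety tables is not determined by the text as it stands.

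**What to change.** Replace the sentence in SAP 9.9.1 with wording such as: *All Safety Population subjects are included in the entire treatment period and in their first treatment period; a subject is included in a later period if he or she received at least one dose of SD-809 in that period, whether or not a visit occurred.* Align the period starts and ends in SAP 7.2 and 8.8. The separate restriction that 7.2 places on the Extended Dose-Adjustment Period (Switch subjects adjusted between Weeks 4 and 8) is a different matter and should be stated alongside.

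The cost is one sentence and a reconciliation of two lists, with no new data. There is a small downside: subjects never assessed after dosing count as event-free unless an event is reported, which slightly dilutes incidence. A footnote giving the number of included subjects with no post-dose contact in the period would make that visible.
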